Appendix 8 Medications used in MS and Determination Criteria

Any medication used for MS along with its category will be retrieved from the eCRF Concomitant medication form. However, the information in the table below will be used to defined subcategory of interest.

MS medications type	WHO-DD Therapeutic class	Standardized Medication name	ATC code	Verbatim term	Comments
Antispasticity medication	Muscle relaxant (M03)	Baclofen	M03BX01	Contains: "BACLOFEN"	
		Tizanidine	M03BX02	Contains: ''TIZANIDINE'''	
		Dantrolene	M03CA	Contains: 'DANTROLENE'	
		Tetrazapam (BDZ)	M03BX07		Not considered as a BDZ in the coding of ATC, but as a centrally acting muscle relaxant.
		Botulinum toxin	M03AX01	Contains: 'BO' and 'Tox' Dysport' 'Xeomin'	
		Others	M03B and M03C apart those mentioned above		Refers to the broader group of muscle relaxants
	Antiepileptic (N03)	Clonazepam	N03AE		N03AE is a BDZ
		Gabapentin	N03AX12		
		Pregabaline	N03AX16		
		Cannabinidiol	N03AX24		Not allowed per protocol
	Psychoanaleptic	Clozapine (BDZ)	N05AH02		
	(NU5)	Benzodiazepines	N05BA N05CD		N05BA and N05CD refers to a list of BDZ
Medication to treat other MS symptoms	Other system nervous system drug (N07)	Dalfampridine	N07XX007		
		Fampridine	N07XX007		

MS=Multiple sclerosis; ATC= Anatomic Therapeutic Class; BDZ=Benzodiazepines

Addendum to Statistical Analysis Plan (SAP)

Protocol Title:	A Double-blind, Randomized, Placebo-controlled, Parallel-group Trial of the Efficacy and Safety of Nabiximols Oromucosal Spray as Add-on Therapy in Patients with Spasticity Due to Multiple Sclerosis
Study Code:	GWSP18023
Protocol Version No. /Date:	V5.0 / 01JUN2021
CRF Version No. / Date:	V3.0 / 05NOV2021
SAP Version No. / Date:	V1.0 / 22MAR2022
SAP Addendum Version No. / Date	V1.0 / 17FEB2023

2.0 Change History

Version/Date	Change Log
1.0 / 17FEB2023	Created as new

GW Pharma Limited	GW	Pharma	Limited
-------------------	----	--------	---------

4.0 Purpose

This addendum to the SAP describes the reporting and analyses of data collected under Protocol GWSP18023 V5.0 dated 01JUN2021 following the early termination of the study.

5.0 Scope

This addendum supplements the SAP.

6.0 Introduction

This SAP addendum should be read in conjunction with the study protocol V5.0 01JUN2021, CRF V3.0 05NOV2021 and SAP V1.0 22MAR2022.

Final approval of the SAP addendum will occur prior to study unblinding.

The decision was made on 9th November 2022 to discontinue the study and halt any further enrollment of patients without the planned number of patients being recruited. As a result of this, an abbreviation of the planned analysis and reporting as detailed in the protocol and SAP will be carried out. The possibility of early termination was described in Protocol Section 16.1.

7.0 Statistical Methods

The abbreviated reporting will follow the strategy as detailed in **Table 7-1**. Although the study will terminate early, the primary hypothesis will still be tested as per the final SAP.

Addendum to Statistical Analysis Plan for Protocol GWSP18023 (17-FEB-2023)

Table 7-1 Strategy for abbreviated reporting

Hierarchy	Strategy	Endpoint	Relevant Sections of SAP V1.0 to be Used
Primary & C Secondary Efficacy s Endpoints ((n	Conduct primary inferential analysis, standard descriptive statistics and listing. Sensitivity and supplemental (including subgroup analyses) will not be conducted. Figures will not be produced.	Daily spasm count	12.5.2.1 & 12.5.2.4
		MSSS-88	12.5.3.1 & 12.5.3.4
Secondary Safety Endpoints (excluding PK)	As described in SAP with the exception of figures, subgroup summaries, repeats on FAS.and those specific to an endpoint (detailed in final column).	TEAEs Clinical laboratory tests	 12.8.1 & 12.8.2 Excluding the following summaries: by time of first onset by AE duration of TEAEs related to IMP by maximum severity of TEAEs related to IMP and leading to IMP discontinuation by maximum severity of serious TEAEs related to IMP 12.8.3 Excluding the following summaries: Values outside of normal ranges Shift tables based on CTCAE v5.0 grade Shift tables based on normal range indicator will be presented by visit rather than by most extreme value and last
		Vital signs	on-treatment value.
		FCG	12.0.7
		C-SSRS	12.8.5.3
Secondary Safety Endpoints (PK)	No processing, analyses or reporting	PK	NA

Addendum to Statistical Analysis Plan for Protocol GWSP18023 (17-FEB-2023)

Exploratory	Listings only, no descriptive or	MSSS-88 subscales	12.5.3.4
Endpoints	inferential statistics or figures.	NRS spasm severity	12.5.4.2
		NRS spasticity	12.5.4.3
		T25FW	12.5.4.4
		SF-36	12.6.1
Other data	As described in SAP with the	Disposition	12.1
e s tł	exception of figures, subgroup summaries, repeats on FAS and those specific to a section (detailed in final column).	Demographics	12.2.1
		Disease Characteristics	12.2.5
		Medical History	12.2.4
		Prior and Concomitant	12.3.2
		Medications and	Excluding summaries of post-treatment medications
		Therapy	
		Treatment Exposure	12.3.1
		Protocol deviations	12.4
			Excluding summaries of major IPDs
		Other Safety	12.8.5.1, 12.8.5.4, 12.8.5.5, 12.8.5.6, 12.8.5.7
		Monitoring of Drug	12.8.6
		Abuse Liability	Excluding the summary of triggered events
	1		

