#### 13.6.5.2 Adverse Events

AEs will be coded according to the MedDRA.

A TEAE is one that started, or worsened in severity or seriousness, following the first dose of IMP.

Descriptive presentations of TEAEs will be given by PT and SOC for the safety analysis set. The number of patients reporting at least 1 TEAE will be provided.

The following summaries will be produced at a minimum:

- All-causality TEAEs
- Treatment-related TEAEs
- All-causality TEAEs by maximal severity
- All-causality serious TEAEs
- Treatment-related serious TEAEs
- TEAEs reported as leading to permanent cessation of IMP
- Fatal TEAEs

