12.8.1.2 Overall Adverse Event Summary

An overall adverse event summary will provide, by treatment arm, the number of adverse events as well as the number and percentage of patients with at least AE in the following categories:

- TEAE
- TEAE related to IMP
- Confirmed or suspected COVID-19 TEAE, (as described in Section 10.23.2)
- TEAE leading to permanent IMP discontinuation
- TEAE related to IMP leading to permanent IMP discontinuation
- Serious TEAE
- Serious TEAE related to IMP
- AE with outcome of death
- AE with outcome of death related to IMP.

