12.8.1.3 All-causality Treatment-emergent Adverse Event Summaries

Descriptive presentations of TEAEs will be given by PT and SOC for the SAF. The number and percentage of patients reporting at least 1 will be provided by treatment arm. As appropriate, the number of adverse events by SOC and PT will also be added.

- All TEAEs by SOC and PT
- All TEAEs by SOC, PT and subgroups (as described in Table 9.3-3)
- *Most common TEAEs (incidence ≥ 2 % in either treatment arm) by SOC and PT
- *Most common TEAEs (incidence ≥ 2 % in either treatment arm) by SOC, and PT and subgroups (as described in Table 9.3-3)
- All TEAEs by SOC, PT and maximum severity
- All TEAEs by SOC, PT and worst action taken on IMP
- All TEAEs by SOC, PT and time of first onset of AE categorized as:
- 1-7 day, 8 to 14 days, 15 to 28 days, 29 to 42 days, 43 to 84 and > 84 days (as described in Section 10.23.3)

- All TEAEs by SOC, PT and AE duration, categorized as:
- 1-7 day, 8 to 14 days, 15 to 28 days, 29 to 42 days ,43 to 84 days ,> 84 days, ongoing, indeterminate (as described in Section 10.23.4)
- All TEAEs by SOC, PT and relationship to IMP
- All treatment-related TEAEs by SOC and PT and maximum severity
- All treatment-related TEAEs by SOC and PT and subgroups (as described in Table 9.3-3)
- All treatment-related TEAEs leading to permanent IMP discontinuation by SOC and PT
- All TEAEs leading to permanent IMP discontinuation by SOC and PT
- All TEAEs leading to permanent IMP discontinuation by SOC and PT and subgroups (as described in Table 9.3-3)
- All treatment-related TEAEs leading to permanent IMP discontinuation by SOC and PT and maximum severity
- All non-serious TEAEs by SOC and PT

* These tables will not present the number of AEs by SOC/PT per treatment arm

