12.8.2.2 Serious Adverse Events

Descriptive presentations of serious TEAEs will be given by PT and SOC for the SAF. The number and percentage of patients reporting at least one serious TEAE, as well as the number of events, within a given treatment arm will be provided as described below:

- All serious TEAEs by SOC and PT,
- All serious TEAEs by SOC, PT and subgroups (as described in Table 9.3-3),
- All serious TEAEs leading to permanent IMP discontinuation by SOC and PT,
- All serious treatment-related TEAEs by SOC and PT,
- All serious treatment-related TEAEs by SOC and PT leading to permanent IMP discontinuation by SOC and PT.

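### On the reading of Table 7-1 that fits the SAP, the addendum drops the SOC/PT table of related serious TEAEs, which the protocol sets as a minimum output

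*SAP*

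**What the plan says.** **Protocol 13.6.5.2 (Adverse Events)** sets the format: "Descriptive presentations of TEAEs will be given by PT and SOC for the safety analysis set". It then introduces a list of seven outputs with "The following summaries will be produced at a minimum". The fifth is "Treatment-related serious TEAEs".

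**SAP V1.0, 12.8.2.2 (Serious Adverse Events)** plans the matching table: "All serious treatment-related TEAEs by SOC and PT". Under SAP 12.8, safety analyses use the safety analysis set (SAF) by actual treatment arm.

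**SAP addendum, 7.0, Table 7-1, TEAEs row** keeps SAP 12.8.1 and 12.8.2 with a short list of exclusions. The last words of that list are "of serious TEAEs related to IMP". Section 6.0 of the addendum explains that the study was stopped before full recruitment and that the reporting set out in the protocol and SAP is therefore abbreviated. Neither section mentions the protocol's minimum list.

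**The concern.** A list headed as a minimum is a floor. An addendum to the SAP can trim outputs that the SAP added above that floor. Here it appears to remove one of the seven that the protocol itself requires, and gives no reason specific to that table.

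TEAE frequency is a stated secondary endpoint. The table concerned shows, for each arm, which kinds of serious event were judged related to the IMP. Protocol 12.2 also requires a positive COVID-19 test to be recorded as an SAE, so the all-causality serious table may mix such events with suspected drug effects. The relatedness filter is what separates them. Under protocol section 14 there is no data safety monitoring committee, so the between-arm review of these events rests largely on the final report.

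**Working it through.** No figure in the plan is at issue, so the check compares texts.

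**Step 1: where the exclusions begin and end.** The bullet breaks in Table 7-1 did not survive text extraction. Three ways of dividing the words were compared with the tables planned in SAP 12.8.1.3 and 12.8.2.2.

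| Reading | Exclusions | Fit with SAP V1.0 |
|---|---|---|
| A | (1) by onset time; (2) by duration; (3) related TEAEs by maximum severity; (4) related TEAEs leading to discontinuation, by maximum severity; (5) related serious TEAEs | All five match planned summaries |
| B | (1) by onset time; (2) by duration; (3) all related TEAEs; (4) maximum severity of related TEAEs leading to discontinuation; (5) maximum severity of related serious TEAEs | (5) matches nothing planned; (3) would remove a different protocol-minimum item |
| C | (1) by onset time; (2) duration of related TEAEs only; (3) maximum severity of related TEAEs leading to discontinuation; (4) maximum severity of related serious TEAEs | (2) and (4) match nothing planned |

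Under reading A, exclusion 3 corresponds to "All treatment-related TEAEs by SOC and PT and maximum severity", exclusion 4 to "All treatment-related TEAEs leading to permanent IMP discontinuation by SOC and PT and maximum severity" and exclusion 5 to "All serious treatment-related TEAEs by SOC and PT". Only A fits throughout. Under C the related serious table would be kept and the conflict would disappear, so the original layout should be checked.

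**Step 2: the seven protocol minimum summaries under reading A.**

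| Protocol 13.6.5.2 item | Table in the SAP | After the addendum |
|---|---|---|
| All-causality TEAEs | 12.8.1.3 | Kept |
| Related TEAEs | 12.8.1.3, by relationship to IMP | Kept |
| All-causality, by maximum severity | 12.8.1.3 | Kept |
| All-causality serious | 12.8.2.2 | Kept |
| Related serious | 12.8.2.2 | **Excluded** |
| Leading to permanent cessation of IMP | 12.8.1.3 | Kept |
| Fatal | 12.8.2.1 | Kept, if at least 2 patients are affected |

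Covered by a SOC/PT table: 7 − 1 = 6 of 7.

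**Step 3: whether the kept outputs supply the missing one.**

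- The overall summary (SAP 12.8.1.2) has one line, "Serious TEAE related to IMP", with events and patients by arm. It gives no event type.
- The serious table and the relationship table are two margins. Counting events for one preferred term in one arm, let n be all events, s the serious ones and r the related ones. The number both serious and related can lie anywhere from max(0, s + r − n) to min(s, r). The overall line fixes only the sum of these numbers across terms, so in general the breakdown cannot be recovered.
- The table of related deaths (12.8.2.1, if at least 2 patients) covers only a subset. So would the table of related serious events leading to discontinuation (12.8.2.2), if the exclusion does not reach it as well.
- The SAE listing (12.8.1.1) carries SOC, preferred term, relatedness and seriousness and is sorted by actual arm, so a hand tally is possible. SAP 12.8.1 counts missing causality as related in summaries but lists the actual value. A tally that ignores this rule could differ from the overall count.

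**The case against.** The strongest reply is that little is lost. Serious event types are still tabulated by arm, related events are still tabulated by SOC and PT, the number of related serious events is still given by arm, and every such event can be found in the listing. A cluster of serious events in one organ class would show in the all-causality serious table. This stands. A reader might infer that the arms can no longer be compared on serious event types, or that the data on related serious events disappear; the retained outputs contradict both.

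A second reply is that the reduction is open. The addendum states that reporting is abbreviated and that its final approval precedes unblinding, and protocol section 13 requires deviations from the original SAP to be described in the clinical study report. This stands as well: the documents do not support an inference of concealment or of a choice driven by results. But a general statement does not identify this departure, and describing a deviation afterwards does not produce a required summary.

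A third reply is that the protocol item carries no SOC/PT qualifier of its own, so the overall line might count as the summary. That is arguable. However, the sentence on presentation by PT and SOC comes just before the list in the same section, and SAP V1.0 implemented the item as a SOC/PT table.

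Finally, the bullet breaks are inferred. That lowers confidence but does not make another reading more likely.

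**Conclusion.** The point holds in a limited form. On the reading that matches SAP V1.0, the addendum removes one of the protocol's seven minimum TEAE summaries: related serious TEAEs by event type and arm. The kept summary tables cannot in general reproduce it, although the listing allows it to be rebuilt by hand.

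Severity is minor and confidence medium. The conclusion assumes that reading A of Table 7-1 is confirmed by the original layout, and that the protocol's PT/SOC sentence governs its list. The practical size depends on how many serious TEAEs were judged related, which the documents do not give. If there were none in either arm, the table would be empty and nothing would be lost.

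**What to change.** Check the bullet layout of Table 7-1 in the original addendum. If reading A is confirmed, delete the exclusion "of serious TEAEs related to IMP" from the TEAEs row, so that the SAP 12.8.2.2 table of related serious TEAEs by SOC and PT is produced by actual treatment arm on the SAF. If the layout shows reading B, restore the related-TEAE summary instead, since that would then be the minimum item removed.

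The cost is one extra table, obtained by applying a relatedness filter to the retained serious-TEAE table, and a change to addendum wording only. The table is already specified in SAP V1.0, so restoring it introduces no new analysis. If the sponsor prefers to leave it out, the addendum should name this departure from Protocol 13.6.5.2 and give the reason.

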#### 13.6.5.3 Clinical Laboratory Data

Clinical laboratory data at Screening, during, and at the end of treatment and the change from baseline to end of treatment will be summarized for the safety analysis set using appropriate summary statistics. Categorical shift tables will also be presented showing the numbers of patients with values outside the normal range. Changes from baseline to each visit will be summarized.

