10.2.4 Reporting of Longitudinal Safety Assessments

Physical examination, serum urine pregnancy test, dipstick urinalysis, examination of oral mucosa, vital signs, body weight, 12-lead ECG, clinical laboratory blood sampling, C-SSRS, MUS will be summarized using the nominal visit. In case of repeat assessments, the original assessment will be used in summaries, but all assessments will be listed.

For patients that discontinued IMP early but remained on study, assessments taken after IMP End Date will be assigned to the Follow-up visit, as long as they are within 30 days of IMP End Date.

For examination of oral mucosa, vital signs, body weight, 12-lead ECG, clinical laboratory blood sampling and C-SSRS the last on-treatment assessment will also be identified. The last on-treatment assessment is defined as the last scheduled assessment prior to IMP End Date, only assessments after the IMP Start Date will be considered (see Section 10.1 for source of dates).

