12.8.3 Laboratory Data

The clinical safety laboratory data (hematology and biochemistry) are planned to be collected at Screening, Visit 2, Visit 4 and Visit 6.

For the purposes of summarization in both the tables and listings, all laboratory values will be converted (as needed) to SI units. The investigator and trial monitor will be provided with a list of the normal ranges used by the central clinical laboratory for all variables assessed during the trial and a statement of accreditation (or similar) for the laboratory.

Only scheduled laboratory parameters defined in Table 9.3-3 coming from central laboratory and those derived from them as eGFR (as defined in Section 10.14) will be included in summary tables. However unscheduled laboratory values (coming from central or local laboratories) will be used in abnormality summary tables and will be presented in listings (using categories as defined in Appendix 2).

Baseline, Visit 4, Visit 6, minimal, maximal and last on-treatment values along with the change from baseline to Visit 4, Visit 6, minimal, maximal and last on-treatment assessment will be summarized using the SAF, by treatment arm, separately for red blood cells parameters and white blood cells parameters, hepatobiliary parameters, renal parameters, coagulation parameters and electrolytes and proteins (as described Appendix 1). Furthermore AST, ALT, GGT, ALP and total bilirubin will also be summarized as a multiple of the upper limit of normal (ULN). The definitions for minimal and maximal values are given in Section 10.24.2 and the definition for last on-treatment value is given in Section 10.24.

Laboratory, hematology and biochemistry (as described in Appendix 1) abnormalities will be evaluated, on patients from the SAF using shift tables from baseline to the last on-treatment value and on the most extreme on-treatment value (as defined in Section 10.24.2) during the 12-week on-treatment period according to baseline status with categories based on:

- Reference ranges as either normal, below the lower limit of normal (LLN) as "Low" or above the ULN as "High"
- CTCAE toxicity grade using version 5.0 or higher (as defined in Appendix 3 for hematology parameters and in Appendix 4 for biochemistry and urinalysis parameters),

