Additionally, shift tables by treatment arm on patients from the SAF will be used to present change in status category (as defined in Section 10.14) for eGFR from baseline to last on-treatment value and to the lowest value during the 12-week on-treatment period.

Furthermore, a summary of patients with laboratory values outside the reference ranges at baseline and during the 12-week on-treatment period (as defined in Section 10.2.2) will be presented for scheduled parameter including either scheduled visit only or scheduled and unscheduled visits, by treatment arm.

Regarding AST, ALT, GGT, ALP and total bilirubin these parameters will be summarized by treatment arm within the SAF for the 12-week on-treatment period using SI units and as a proportion of the population with no missing assessment if abnormal values with reference to ULN are presented using the categories as described in Table 12.8-1.

Hepatic laboratory Parameters	Abnormality criteria
ALT	> 3 x ULN
	>5 x ULN
	> 8 x ULN
	> 10 x ULN
	> 20 x ULN
AST	> 3 x ULN
	>5 x ULN
	> 8 x ULN
	> 10 x ULN
	> 20 x ULN
ALP	> 1.5 x ULN
	> 2 x ULN

Table 12.8-1 Hepatic Abnormality Criteria

	> 3 x ULN
Total bilirubin	> 1.5 x ULN
	> 2 x ULN
	> 3 x ULN
	> 5 x ULN
GGT	> 1 x ULN

ALT = alanine aminotransferase; *AST* = aspartate aminotransferase; *ALP* = alkaline phosphatase; *GGT*= gamma-glutamyl transferase.

All laboratory values will be listed and all test values outside the normal range will be flagged.

• Urinalysis results, planned to be collected at Screening and Day 85 (end of treatment) will be summarized and listed

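### The addendum's by-visit laboratory shift tables leave no count by arm of patients with any out-of-range value on treatment, for parameters outside the hepatic and eGFR tables

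*SAP*

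**What the plan says.** SAP 12.8.3 (Laboratory Data) planned to evaluate hematology and biochemistry abnormalities "using shift tables from baseline to the last on-treatment value and on the most extreme on-treatment value", with categories based on the reference range and on CTCAE grade. It also planned "a summary of patients with laboratory values outside the reference ranges at baseline and during the 12-week on-treatment period", by arm, in a version for scheduled visits and a version that adds unscheduled visits.

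SAP Addendum 7.0, Table 7-1, keeps section 12.8.3 for laboratory tests with three changes:

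- The summary listed as "Values outside of normal ranges" is dropped.
- The CTCAE-grade shift tables are dropped.
- "Shift tables based on normal range indicator will be presented by visit rather than by most extreme value and last" on-treatment value.

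SAP 10.2.4 summarizes laboratory data by nominal visit and, where a test was repeated, uses the original result. For patients who stop IMP early but remain on study, "assessments taken after IMP End Date will be assigned to the Follow-up visit, as long as they are within 30 days" of that date. SAP 10.2.2 sets the on-treatment period for safety from IMP start to IMP End Date plus 30 days. Post-baseline laboratory samples are scheduled only at Visit 4 (Day 29) and Visit 6 (Day 85).

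Protocol 13.6.5.3 states: "Categorical shift tables will also be presented showing the numbers of patients with values outside the normal range".

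**The concern.** The most-extreme-value shift and the out-of-range summary each answered a simple safety question: how many patients in each arm had an abnormal result at any time on treatment? A by-visit shift table answers a different one: of those with a sample at this visit, how many were abnormal at it?

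The two can differ in a way related to tolerability. Protocol section 10 lets the investigator stop IMP for an adverse event, including a clinically significant laboratory result, and asks that the patient remain in the trial. If such a result came from an unscheduled sample before Visit 4, it would appear in neither the Visit 4 nor the Visit 6 row. The protocol provides for no data safety monitoring committee (section 14), so the final report is where the arms are compared.

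**Working it through.** The plan states no figure on this point, so there is none to reproduce. The check sets the rules side by side and traces where each scheduled sample goes.

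**1. Scheduled samples of patients who stop IMP early and stay in the trial.** Inputs: Visit 4 on Day 29 and Visit 6 on Day 85 (Protocol Appendix 1), the Follow-up rule (SAP 10.2.4) and the 30-day safety window (SAP 10.2.2). Let gap = visit day − IMP stop day.

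- Gap of 0 or less: the sample keeps its visit.
- Gap of 1 to 30: it moves to Follow-up but lies inside the on-treatment window that the V1.0 tables used.
- Gap above 30: it has no place under either version.

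| IMP stop day | Visit 4 sample (Day 29) | Visit 6 sample (Day 85) |
|---|---|---|
| 1–28 | gap 1–28: Follow-up; inside V1.0 window | gap 57–84: not reported; outside V1.0 window |
| 29–54 | gap 0 or less: Visit 4 | gap 31–56: not reported; outside V1.0 window |
| 55–84 | gap below 0: Visit 4 | gap 1–30: Follow-up; inside V1.0 window |

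The addendum therefore affects two groups of scheduled samples: Visit 4 after a stop on Days 1–28, and Visit 6 after a stop on Days 55–84. Only patients in the first row can be missing from both visit rows.

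The visit windows move these boundaries. Visit 4 may fall on Days 26–32, so the first boundary lies between Days 26 and 32. Visit 6 may fall on Days 78–92, so the second lies between 78 − 30 = Day 48 and 92 − 30 = Day 62.

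**2. Is there a Follow-up row?** SAP 12.8.3 names Visits 4 and 6 as the post-baseline visits for laboratory summaries, and no laboratory sample is scheduled at Visit 7. The addendum says only that the tables are by visit.

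**3. Unscheduled results.** SAP 12.8.3 lets unscheduled values feed abnormality summary tables, but the out-of-range summary is the place that expressly includes unscheduled visits. It is now cancelled. A by-visit table under the nominal-visit rule has no place for them.

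**4. Patients with both samples.** Suppose a patients are out of range at Visit 4 and b at Visit 6. The number out of range at either visit can be anything from the larger of a and b up to a + b (capped at the arm size). The by-visit tables do not fix it.

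**5. What remains under Table 7-1.**

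- Counts by multiples of ULN for ALT, AST, ALP, GGT and bilirubin (SAP Table 12.8-1)
- The count of patients meeting DILI criteria (SAP 12.8.3.1)
- The eGFR category shift to the last and lowest on-treatment value
- Continuous summaries of minimum, maximum and last on-treatment values
- Listings with out-of-range flags, and treatment-emergent adverse event tables

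None of these counts patients with any out-of-range hematology, electrolyte, protein, creatinine or urea value. Albumin belongs with the proteins here: SAP Appendix 1 files it as hepatobiliary, but Table 12.8-1 does not cover it.

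**The case against.** The best defence is that this is a reporting choice in an abbreviated report, with approval due before unblinding. SAP 10.2.4 reassigns samples to Follow-up and does not delete them. Table 7-1 does not exclude Follow-up, and since no laboratory sample is scheduled at Visit 7, the reassignment has little purpose for laboratory data unless that row is reported. Abnormal results judged to be adverse events also reach the adverse event tables.

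Much of this stands. If a Follow-up row is shown, the scheduled samples identified above are recovered. It still gives no any-time count per patient and takes in no unscheduled results, and the text does not promise it.

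A reader might infer more than the documents support:

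- **That categorical laboratory counts by arm are lost altogether.** The hepatic, DILI and eGFR tables remain and run over the on-treatment period.
- **That early stoppers in general disappear.** Patients who leave the trial have withdrawal samples at nominal Visit 6, and those who stop after Visit 4 keep their Visit 4 row.
- **That the addendum removes Visit 6 samples taken more than 30 days after stopping.** V1.0 already excluded them.
- **That dropping the last-on-treatment shift loses unscheduled results.** SAP 10.2.4 already limited it to scheduled assessments.
- **That the protocol is contradicted.** It promises categorical shift tables without requiring the most extreme value, and by-visit tables meet that wording.

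**Conclusion.** The point holds as a limited loss of safety information that is cheap to repair. For hematology, electrolytes, proteins, creatinine and urea, the abbreviated report would contain no count by arm of patients with any out-of-range value during the on-treatment period.

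The share of patients missing from both the Visit 4 and Visit 6 rows equals the share who stop IMP before Visit 4 and stay in the trial, if no Follow-up row is shown. The documents give no early-stopping rate by arm, so I put no number on it. It might be inferred that a treatment difference would be understated. The loss can differ by arm because it is linked to tolerability, but neither its direction nor its size can be derived from the documents.

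The conclusion rests on two readings: that the cancelled item on values outside normal ranges is the SAP 12.8.3 reference-range summary and not Table 12.8-1, and that by-visit means the visits named in 12.8.3. If the cancelled item also covered Table 12.8-1, the loss would be larger. If Follow-up is included, only the any-time count and the unscheduled results are lost.

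**What to change.** In the laboratory row of Table 7-1, do one of the following:

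- Reinstate the SAP 12.8.3 summary of patients outside the reference range over the on-treatment period, by arm, in its version with scheduled and unscheduled visits. This is the cleaner choice because its wording already includes unscheduled visits.
- Use the V1.0 normal-range shift to the most extreme on-treatment value as the single shift table in place of the by-visit display, and state whether unscheduled results enter it.

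If the by-visit tables are kept, include the Follow-up row and say so.

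The cost is small: at most one additional table, already specified in SAP V1.0, in a report meant to be short. The second option replaces a display and need not add one.
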